### **11.4.2.3 Multiplicity considerations**

Not applicable: all analyses are descriptive without test.

### **11.4.3 Analyses of safety data**

All safety analyses will be performed on the safety population using the following common rules:

The following definitions will be applied to laboratory parameters and vital signs

- The potentially clinically significant abnormality (PCSA) values are defined as abnormal values considered medically important by the Sponsor according to predefined criteria/thresholds based on literature review and defined by the Sponsor for clinical laboratory tests, vital signs. These abnormal values will be detailed in the Statistical Analysis Plan that will be validated before the database freezing.
- PCSA criteria will determine which patients had at least 1 PCSA during the on-treatment period, taking into account all evaluations performed during the on-treatment period, including unscheduled or repeated evaluations. The number of all such patients will be the numerator for the on-treatment PCSA percentage.

Death. The following deaths summaries will be generated:

- Number (%) of patients who died by study period (treatment-emergent AEs, on-study) and reasons for death summarized on the safety population
- All AEs leading to death (death as an outcome on the AE CRF/eCRF page as reported by the Investigator), by primary SOC, HLGT, HLT, and PT, showing number (%) of patients sorted by internationally agreed order of SOC and alphabetic order of HLGT, HLT, and PT
- TEAE leading to death (death as an outcome on the AE CRF/eCRF page as reported by the Investigator) by primary SOC, HLGT, HLT and PT showing number (%) of patients sorted by internationally agreed order of SOC and alphabetic order of HLGT, HLT, and PT.

## **11.5 INTERIM ANALYSIS**

Not applicable

## **12 ETHICAL AND REGULATORY CONSIDERATIONS**

### **12.1 ETHICAL AND REGULATORY STANDARDS**

This clinical trial will be conducted by the Sponsor, the Investigator, and delegated Investigator staff and Sub-investigator, in accordance with consensus ethics principles derived from international ethics guidelines, including the Declaration of Helsinki, and the ICH guidelines for good clinical practice (GCP), all applicable laws, rules and regulations.

This clinical trial will be recorded in a free, publicly accessible, internet-based registry, no later than 21 days after the first patient enrollment, in compliance with applicable regulatory requirements and with Sanofi public disclosure commitments.

### **12.2 INFORMED CONSENT**

The Investigator (according to applicable regulatory requirements), or a person designated by the Investigator, and under the Investigator's responsibility, should fully inform the patient of all pertinent aspects of the clinical trial including the written information giving approval/favorable opinion by the ethics committee (IRB/IEC). All participants should be informed to the fullest extent possible about the study, in language and terms they are able to understand.

Prior to a patient's participation in the clinical trial, the written ICF should be signed, name filled in and personally dated by the patient or by the patient's legally acceptable representative, and by the person who conducted the informed consent discussion. A copy of the signed and dated written ICF will be provided to the patient.

The ICF used by the Investigator for obtaining the patient's informed consent must be reviewed and approved by the Sponsor prior to submission to the appropriate ethics committee (IRB/IEC) for approval/favorable opinion.

### **12.3 HEALTH AUTHORITIES AND INSTITUTIONAL REVIEW BOARD/INDEPENDENT ETHICS COMMITTEE (IRB/IEC)**

As required by local regulation, the Investigator or the Sponsor must submit this clinical trial protocol to the health authorities (competent regulatory authority) and the appropriate IRB/IEC, and is required to forward to the respective other party a copy of the written and dated approval/favorable opinion signed by the chairman with IRB/IEC composition.

The clinical trial (study number, clinical trial protocol title and version number), the documents reviewed [clinical trial protocol, ICF, labeling documents (summary of product characteristics, package insert), Investigator's curriculum vitae, etc.] and the date of the review should be clearly stated on the written IRB/IEC approval/favorable opinion.

The IMP will not be released at the study site and the Investigator will not start the study before the written and dated approval/favorable opinion is received by the Investigator and the Sponsor.

During the clinical trial, any amendment or modification to the clinical trial protocol should be submitted to the health authorities (competent regulatory authority), as required by local regulation, in addition to the IRB/IEC before implementation, unless the change is necessary to eliminate an immediate hazard to the patients, in which case the health authorities (competent regulatory authority) and the IRB/IEC should be informed as soon as possible. They should also be informed of any event likely to affect the safety of patients or the continued conduct of the clinical trial, in particular any change in safety. All updates to labeling information, will be sent to the IRB/IEC and to health authorities (competent regulatory authority), as required by local regulation.

A progress report is sent to the IRB/IEC at least annually and a summary of the clinical trial's outcome at the end of the clinical trial.

## **13 STUDY MONITORING**

### **13.1 RESPONSIBILITIES OF THE INVESTIGATOR(S)**

The Investigator is required to ensure compliance with all procedures required by the clinical trial protocol and with all study procedures provided by the Sponsor (including security rules). The Investigator agrees to provide reliable data and all information requested by the clinical trial protocol (with the help of the e-CRF, Discrepancy Resolution Form [DRF] or other appropriate instrument) in an accurate and legible manner according to the instructions provided and to ensure direct access to source documents by Sponsor representatives.

If any circuit includes transfer of data particular attention should be paid to the confidentiality of the patient's data to be transferred.

The Investigator may appoint such other individuals as he/she may deem appropriate as Sub-investigators to assist in the conduct of the clinical trial in accordance with the clinical trial protocol. All Sub-investigators shall be appointed and listed in a timely manner. The Sub-investigators will be supervised by and work under the responsibility of the Investigator. The Investigator will provide them with a copy of the clinical trial protocol and all necessary information.

### **13.2 RESPONSIBILITIES OF THE SPONSOR**

The Sponsor of this clinical trial is responsible to regulatory authorities for taking all reasonable steps to ensure the proper conduct of the clinical trial as regards ethics, clinical trial protocol compliance, and integrity and validity of the data recorded on the eCRFs. Thus, the main duty of the monitoring team is to help the Investigator and the Sponsor maintain a high level of ethical, scientific, technical and regulatory quality in all aspects of the clinical trial.

At regular intervals during the clinical trial, the site will be contacted, through monitoring visits, letters or telephone calls, by a representative of the monitoring team to review study progress, Investigator and patient compliance with clinical trial protocol requirements and any emergent problems. These monitoring visits will include but not be limited to review of the following aspects: patient informed consent, patient recruitment and follow-up, SAE documentation and reporting, AESI documentation and reporting, AE documentation, IMP allocation, patient compliance with the IMP regimen, IMP accountability, concomitant therapy use and quality of data.

### **13.3 SOURCE DOCUMENT REQUIREMENTS**

According to the ICH GCP, the monitoring team must check the eCRF entries against the source documents, except for the pre-identified source data directly recorded in the eCRF. The informed consent form will include a statement by which the patient allows the Sponsor's duly authorized

personnel, the ethics committee (IRB/IEC), and the regulatory authorities to have direct access to original medical records which support the data on the eCRFs (eg, patient's medical file, appointment books, original laboratory records, etc.). These personnel, bound by professional secrecy, must maintain the confidentiality of all personal identity or personal medical information (according to confidentiality and personal data protection rules).

#### **13.4 USE AND COMPLETION OF CASE REPORT FORMS (CRFS) AND ADDITIONAL REQUEST**

It is the responsibility of the Investigator to maintain adequate and accurate eCRFs (according to the technology used) designed by the Sponsor to record (according to Sponsor instructions) all observations and other data pertinent to the clinical investigation in a timely manner. All eCRFs should be completed in their entirety in a neat, legible manner to ensure accurate interpretation of data.

Should a correction be made, the corrected information will be entered in the eCRF overwriting the initial information. An audit trail allows identifying the modification.

Data are available within the system to the Sponsor as soon as they are entered in the eCRF.

The computerized handling of the data by the Sponsor may generate additional requests (DRF) to which the Investigator is obliged to respond by confirming or modifying the data questioned. The requests with their responses will be managed through the eCRF.

#### **13.5 USE OF COMPUTERIZED SYSTEMS**

The complete list of computerized systems used for the study is provided in a separate document which is maintained in the Sponsor trial master file.

## **14 ADDITIONAL REQUIREMENTS**

### **14.1 CURRICULUM VITAE**

A current copy of the curriculum vitae describing the experience, qualification and training of each Investigator and Sub-investigator will be signed, dated and provided to the Sponsor prior to the beginning of the clinical trial.

### **14.2 RECORD RETENTION IN STUDY SITES**

The Investigator must maintain confidential all study documentation, and take measures to prevent accidental or premature destruction of these documents.

The Investigator should retain the study documents at least 15 years after the completion or discontinuation of the clinical trial.

However, applicable regulatory requirements should be taken into account in the event that a longer period is required.

The Investigator must notify the Sponsor prior to destroying any study essential documents following the clinical trial completion or discontinuation.

If the Investigator's personal situation is such that archiving can no longer be ensured by him/her, the Investigator shall inform the Sponsor and the relevant records shall be transferred to a mutually agreed upon designee.

### **14.3 CONFIDENTIALITY**

All information disclosed or provided by the Sponsor (or any company/institution acting on their behalf), or produced during the clinical trial, including, but not limited to, the clinical trial protocol, personal data in relation to the patients, the CRFs, and the results obtained during the course of the clinical trial, is confidential, prior to the publication of results. The Investigator and any person under his/her authority agree to undertake to keep confidential and not to disclose the information to any third party without the prior written approval of the Sponsor.

However, the submission of this clinical trial protocol and other necessary documentation to the ethics committee (IRB/IEC) is expressly permitted, the IRB/IEC members having the same obligation of confidentiality.

The Sub-investigators shall be bound by the same obligation as the Investigator. The Investigator shall inform the Subinvestigators of the confidential nature of the clinical trial.

The Investigator and the Sub-investigators shall use the information solely for the purposes of the clinical trial, to the exclusion of any use for their own or for a third party's account.

#### **14.4 PROPERTY RIGHTS**

All information, documents and IMP provided by the Sponsor or its designee are and remain the sole property of the Sponsor.

The Investigator shall not and shall cause the delegated Investigator staff /Sub-investigator not to mention any information or the Product in any application for a patent or for any other intellectual property rights.

All the results, data, documents and inventions, which arise directly or indirectly from the clinical trial in any form, shall be the immediate and exclusive property of the Sponsor.

The Sponsor may use or exploit all the results at its own discretion, without any limitation to its property right (territory, field, continuance). The Sponsor shall be under no obligation to patent, develop, market or otherwise use the results of the clinical trial.

As the case may be, the Investigator and/or the Sub-investigators shall provide all assistance required by the Sponsor, at the Sponsor's expense, for obtaining and defending any patent, including signature of legal documents.

#### **14.5 DATA PROTECTION**

- The patient's personal data, which are included in the Sponsor database shall be treated in compliance with all applicable laws and regulations
- When archiving or processing personal data pertaining to the Investigator and/or to the patients, the Sponsor shall take all appropriate measures to safeguard and prevent access to this data by any unauthorized third party
- The Sponsor also collects specific data regarding Investigator as well as personal data from any person involved in the study which may be included in the Sponsor's databases, shall be treated by both the Sponsor and the Investigator in compliance with all applicable laws and regulations.

#### **14.6 INSURANCE COMPENSATION**

The Sponsor certifies that it has taken out a liability insurance policy covering all clinical trials under its sponsorship. This insurance policy is in accordance with local laws and requirements. The insurance of the Sponsor does not relieve the Investigator and the collaborators from any obligation to maintain their own liability insurance policy. An insurance certificate will be provided to the IECs/IRBs or regulatory authorities in countries requiring this document.

#### **14.7 SPONSOR AUDITS AND INSPECTIONS BY REGULATORY AGENCIES**

For the purpose of ensuring compliance with the clinical trial protocol, good clinical practice, and applicable regulatory requirements, the Investigator should permit auditing by or on the behalf of the Sponsor and inspection by regulatory authorities.

The Investigator agrees to allow the auditors/inspectors to have direct access to his/her study records for review, being understood that these personnel is bound by professional secrecy, and as such will not disclose any personal identity or personal medical information.

The Investigator will make every effort to help with the performance of the audits and inspections, giving access to all necessary facilities, data, and documents.

As soon as the Investigator is notified of a planned inspection by the authorities, he will inform the Sponsor and authorize the Sponsor to participate in this inspection.

The confidentiality of the data verified and the protection of the patients should be respected during these inspections.

Any result and information arising from the inspections by the regulatory authorities will be immediately communicated by the Investigator to the Sponsor.

The Investigator shall take appropriate measures required by the Sponsor to take corrective actions for all problems found during the audit or inspections.

#### **14.8 PREMATURE DISCONTINUATION OF THE STUDY OR PREMATURE CLOSE-OUT OF A SITE**

##### **14.8.1 By the Sponsor**

The Sponsor has the right to terminate the participation of either an individual site or the study at any time, for any reason, including but not limited to the following:

- The information on the product leads to doubt as to the benefit/risk ratio
- Patient enrollment is unsatisfactory
- The Investigator has received from the Sponsor all IMP, means, and information necessary to perform the clinical trial and has not included any patient after a reasonable period of time mutually agreed upon
- Noncompliance of the Investigator or Sub-investigator, delegated staff with any provision of the clinical trial protocol, and breach of the applicable laws and regulations or breach of the ICH GCP
- The total number of patients are included earlier than expected.

In any case the Sponsor will notify the Investigator of its decision by written notice.

##### **14.8.2 By the Investigator**

The Investigator may terminate his/her participation upon thirty (30) days' prior written notice if the study site or the Investigator for any reason becomes unable to perform or complete the clinical trial.

In the event of premature discontinuation of the study or premature close-out of a site, for any reason whatsoever, the appropriate IRB/IEC and regulatory authorities should be informed according to applicable regulatory requirements.

#### **14.9 CLINICAL TRIAL RESULTS**

The Sponsor will be responsible for preparing a clinical study report and to provide a summary of study results to the Investigator.

#### **14.10 PUBLICATIONS AND COMMUNICATIONS**

The Investigator undertakes not to make any publication or release pertaining to the study and/or results of the study prior to the Sponsor's written consent, being understood that the Sponsor will not unreasonably withhold its approval.

As the study is being conducted at multiple sites, the Sponsor agrees that, consistent with scientific standards, a primary presentation or publication of the study results based on global study outcomes shall be sought. However, if no multicenter publication is submitted, underway, or planned within twelve (12) months of the completion of this study at all sites, the Investigator shall have the right to publish or present independently the results of this study in agreement with other Investigators and stakeholders. The Investigator shall provide the Sponsor with a copy of any such presentation or publication for review and comment at least 30 days in advance of any presentation or submission for publication. In addition, if requested by the Sponsor, any presentation or submission for publication shall be delayed for a limited time, not to exceed 90 days, to allow for filing of a patent application or such other justified measures as the Sponsor deems appropriate to establish and preserve its proprietary rights.

The Investigator shall not use the name(s) of the Sponsor and/or its employees in advertising or promotional material or publication without the prior written consent of the Sponsor. The Sponsor shall not use the name(s) of the Investigator and/or the collaborators in advertising or promotional material or publication without having received his/her and/or their prior written consent(s).

The Sponsor has the right at any time to publish the results of the study.

## **15 CLINICAL TRIAL PROTOCOL AMENDMENTS**

All appendices attached hereto and referred to herein are made part of this clinical trial protocol.

The Investigator should not implement any deviation from, or changes to the clinical trial protocol without agreement by the Sponsor and prior review and documented approval/favorable opinion from the IRB/IEC and/or notification/approval of health authorities (competent regulatory authority) of an amendment, as required by local regulation, except where necessary to eliminate an immediate hazard(s) to clinical trial patients, or when the change(s) involves only logistical or administrative aspects of the trial. Any change agreed upon will be recorded in writing, the written amendment will be signed by the Investigator and by the Sponsor and the signed amendment will be filed with this clinical trial protocol.

Any amendment to the clinical trial protocol requires written approval/favorable opinion by the IRB/IEC prior to its implementation, unless there are overriding safety reasons.

In case of substantial amendment to the clinical trial protocol, approval from the health authorities (competent regulatory authority) will be sought before implementation.

In some instances, an amendment may require a change to the informed consent form. The Investigator must receive an IRB/IEC approval/favorable opinion concerning the revised informed consent form prior to implementation of the change and patient signature should be re-collected if necessary.

## **17 APPENDICES**

## Appendix A Contraceptive guidance and collection of pregnancy information

### DEFINITIONS

#### Woman of childbearing potential (WOCBP)

A woman is considered fertile following menarche and until becoming post-menopausal unless permanently sterile (see below).

#### Women in the following categories are not considered WOCBP

1. Premenarchal
2. Premenopausal female with 1 of the following:
  - Documented hysterectomy
  - Documented bilateral salpingectomy
  - Documented bilateral oophorectomy.
3. Postmenopausal female
  - A postmenopausal state is defined as no menses for 12 months without an alternative medical cause. A high follicle stimulating hormone (FSH) level in the postmenopausal range may be used to confirm a postmenopausal state in women not using hormonal contraception or hormonal replacement therapy (HRT). However, in the absence of 12 months of amenorrhea, a single FSH measurement is insufficient.
  - Females on hormone replacement therapy (HRT) and whose menopausal status is in doubt will be required to use one of the non-hormonal highly effective contraception methods if they wish to continue their HRT during the study. Otherwise, they must discontinue HRT to allow confirmation of postmenopausal status before study enrollment.

### CONTRACEPTION GUIDANCE

#### Female participants

Female participants of childbearing potential are eligible to participate if they agree to use a highly effective method of contraception consistently and correctly as described in the following Table.

**Table 2: Highly Effective Contraceptive Methods**

Highly Effective Contraceptive Methods That Are User Dependenta Failure rate of <1% per year when used consistently and correctly

• Combined (estrogen- and progestogen-containing ) hormonal contraception associated with inhibition of ovulationb

- oral

- intravaginal

- transdermal

• Progestogen-only hormone contraception associated with inhibition of ovulation

- oral

- injectable

Highly Effective Methods That Are User Independenta

• Implantable progestogen-only hormonal contraception associated with inhibition of ovulationb

- Intrauterine device (IUD)

- Intrauterine hormone-releasing system (IUS)

• Bilateral tubal occlusion

Vasectomized partner A vasectomized partner is a highly effective contraceptive method provided that the partner is the sole sexual partner of the WOCBP and the absence of sperm has been confirmed. If not, an additional highly effective method of contraception should be used.
Sexual abstinence Sexual abstinence is considered a highly effective method only if defined as refraining from heterosexual intercourse during the entire period of risk associated with the study treatment. The reliability of sexual abstinence needs to be evaluated in relation to the duration of the study and the preferred and usual lifestyle of the participant.
NOTES:  a) Typical use failure rates may differ from those when used consistently and correctly. Use should be consistent with local regulations regarding the use of contraceptive methods for participants participating in clinical studies.  b) Hormonal contraception may be susceptible to interaction with the study treatment, which may reduce the efficacy of the contraceptive method. In this case TWO highly effective methods of contraception should be utilized during the treatment period and for up to 3 months after treatment after the last dose of study treatment.

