	
RA defined as a DAS28-ESR >3.2 at Screening
 

• Patients with inadequate response within at least the last 3 months or intolerance to current csDMARD or to at least one anti-TNF therapy (as defined by the investigator)

• Oral corticosteroids (<math>\leq 15</math> mg/day prednisone or equivalent) and NSAIDs or COX-2 (up to the maximum recommended dose) are allowed if at a stable dose for at least 4 weeks prior to Baseline

• Permitted csDMARDs are allowed if at a stable dose for at least 4 weeks prior to Baseline

• Females of childbearing potential can participate in this study only if using a reliable means of contraception during the study and for at least 3 months following the last dose of sarilumab

• Female of childbearing potential must have a negative pregnancy test at the Screening and Baseline visits

• Patients must have signed a written informed consent prior to perform any study-related procedures.

 
Exclusion criteria:
 

• Rheumatic autoimmune disease other than RA or prior history or current inflammatory joint disease other than RA

• Treatment with any investigational agent within 4 weeks of Screening

• Last RA treatment prior to inclusion with any antiJAK or biologic DMARD other than anti-TNF

• Patients treated with anti-TNF (e.i. adalimumab, infliximab, certolizumab, golimumab, etanercept) before the screening period, which are maintained within the 4 weeks before the inclusion (i.e.the first injection of sarilumab)

• Intra-articular or parenteral corticosteroids within 4 weeks prior to Baseline

• History of severe allergic or anaphylactic reactions to human, humanized, or murine monoclonal antibodies (or to any of the excipients associated to sarilumab)

• Stage III or IV cardiac failure according to the New York Heart Association classification

• Evidence of active malignant disease, malignancies diagnosed within the previous 10 years (except basal and squamous cell carcinoma of the skin or carcinoma in situ of the cervix uteri previously excised and cured)

• Patient who is institutionalized due to regulatory or legal order or patient who is mentally disabled or educationally disadvantaged

• History of previous gastrointestinal perforation or diverticulitis

• Known active current/ recurrent infections (including

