### **7.2.2 Exclusion criteria related to the current knowledge of Sanofi compound**

- E 11. Pregnant or breastfeeding woman
- E 12. Women of childbearing potential not protected by highly-effective contraceptive method(s) of birth control (as defined in the informed consent form and/or in a local protocol addendum/amendment) over the study period and for at least 3 months following the last dose of sarilumab, and/or who are unwilling or unable to be tested for pregnancy
- E 13. History of severe allergic or anaphylactic reactions to human, humanized, or murine monoclonal antibodies (or to any of the excipients associated to sarilumab)
- E 14. Immunization with a live/attenuated vaccine within 4 weeks prior to Baseline
- E 15. Stage III or IV cardiac failure according to the New York Heart Association classification
- E 16. History of previous gastrointestinal perforation or diverticulitis
- E 17. Known active current/ recurrent infections (including but not limited to active tuberculosis [TB] or history of incompletely treated TB and atypical mycobacterial disease, hepatitis B and C, and herpes zoster)  
  
NOTE: in case of latent TB infection the patient may be included if a subsequent appropriate anti TB treatment is initiated since at least 3 weeks
- E 18. Positive hepatitis B surface antigen (HbsAg), and/or positive total hepatitis B core antibody, and/or positive hepatitis C antibody (HCV) at the Screening visit
- E 19. Evidence of serious uncontrolled concomitant disease, including severe uncontrolled hypercholesterolemia or hypertriglyceridemia
- E 20. Patients with any of the following laboratory abnormalities at the Screening or Baseline visit:

- Hemoglobin <8.5 g/dL
- White blood cells <3000/mm^3
- Absolute neutrophil count <2000/mm^3
- Absolute lymphocyte count <500/mm^3
- Platelet count <150 000 cells/mm^3
- Creatinine clearance <30 mL/min
- AST or ALT >1.5 x ULN.
- Bilirubin (total) >ULN, unless Gilbert's disease has been determined by genetic testing and has been documented
- Total fasting cholesterol >3.50 g/L [9.1 mmol/L]) or triglycerides >5.00 g/L [5.6 mmol/L])

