### 8.8.3 Drug interactions

In vitro studies demonstrate that IL-6 reduces cytochrome CYP1A2, CYP2C9, CYP2C19, and CYP3A4 enzyme expression. Caution should be exercised in patients who will start sarilumab treatment while on therapy with CYP3A substrates (e.g. oral contraceptives or statins).

Sarilumab or tocilizumab, which antagonize IL-6, may normalize the formation of CYP450 enzymes. As a result, the therapeutic effect of drugs that are metabolized by these CYP450 isoforms may decrease when RA patients start receiving sarilumab. CYP450 substrates with a narrow therapeutic index should be monitored in patients that enter the treatment period. Some examples of CYP450 substrates with a narrow therapeutic index that require therapeutic monitoring (pharmacodynamics and/or drug concentration) include: warfarin, cyclosporine, theophylline, digoxin, antiepileptics like carbamazepine (Carbatrol®, Tegretol®), divalproex (Depakote®), phenytoin (Dilantin®), or valproic acid (Depakene®); or antiarrhythmics, like disopyramide (Norpace®), procainamide (Procan®, Pronestyl®), or quinidine (Quinidex®, Quin-Release Quin-G®).

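### Appendix A, Table 2, note b sets a ceiling but no floor on how long the second contraceptive method continues after the last dose

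*Protocol*

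**What the plan says.** Four places in the documents deal with contraception after the last dose.

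- **Protocol Appendix A, Table 2, note b.** The note gives its reason first: "Hormonal contraception may be susceptible to interaction with the study treatment, which may reduce the efficacy of the contraceptive method". In that case it asks for two highly effective methods, which "should be utilized during the treatment period and for up to 3 months after treatment after the last dose of study treatment".
- **Protocol 7.2.2, E 12.** This excludes women of childbearing potential who are not protected by highly effective contraception "over the study period and for at least 3 months following the last dose of sarilumab". The acceptable methods are those "as defined in the informed consent form and/or in a local protocol addendum/amendment".
- **Protocol synopsis, inclusion criteria.** Women of childbearing potential must use reliable contraception "during the study and for at least 3 months following the last dose of sarilumab".
- **SAP 1.3.** E 12 is repeated with the same duration.

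Two other texts bear on how note b is read. The guidance for female participants in Appendix A makes women of childbearing potential "eligible to participate if they agree to use a highly effective method of contraception consistently and correctly as described in the following Table". Section 8.8.3 on drug interactions warns that "the therapeutic effect of drugs that are metabolized by these CYP450 isoforms may decrease when RA patients start receiving sarilumab", and it names oral contraceptives among the drugs concerned.

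Section 15 makes the appendices part of the protocol, so note b is an operative instruction and not background material.

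**The concern.** The second method exists to cover a possible loss of efficacy in the first. Note b says when this cover starts and the latest point to which it need run. It does not say how long it must last once dosing has stopped. Everywhere else that the documents set a post-dose period for contraception, three months is a minimum.

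At stake is the protection of a woman on hormonal contraception in the weeks after her last injection. A site that applies note b literally could let her drop the second method early. The last scheduled pregnancy test is at the post-treatment visit, 2 to 4 weeks after the last dose (Protocol 10.1.6), so most of the three-month period falls after scheduled follow-up has ended. In that time she depends on the instruction she was given. The protocol treats pregnancy as an adverse event of special interest, with notification within 24 hours and mandatory follow-up to outcome (Protocol 10.4.1.3).

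**Working it through.** No arithmetic applies. The check is a comparison of the texts.

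| Text | What it governs | Bound after the last dose |
|---|---|---|
| Appendix A, Table 2, note b | the second method, added to hormonal contraception that may be weakened | at most 3 months |
| Protocol 7.2.2, E 12 | highly effective contraception overall | at least 3 months |
| Protocol synopsis | reliable contraception overall | at least 3 months |
| SAP 1.3, E 12 | as protocol E 12 | at least 3 months |

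**Step 1: can the rules be followed together?** Yes. A woman who uses one method for three months or longer, and a second for any part of that time up to three months, satisfies all four rows.

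**Step 2: does following them together close the gap?** Take a woman on a combined oral contraceptive, a type that carries marker b in the table. She uses a second method throughout treatment, stops it before three months have passed since the last dose, and continues the oral contraceptive for the full three months.

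- Synopsis: met, since she uses contraception for the whole period.
- E 12: met on the protocol's own list, because Table 2 classes combined hormonal contraception as highly effective. The consent form or a local addendum could say otherwise.
- Note b: met, because her use of the second method did not exceed three months.

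She complies with every sentence. For the last part of the period she relies only on the type of method whose efficacy note b says may be reduced.

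**Step 3: does another section supply the missing minimum?** Section 8.8.3 says "Caution should be exercised in patients who will start sarilumab treatment while on therapy with CYP3A substrates (e.g. oral contraceptives or statins", but it mentions no second method and no duration. The general guidance in Appendix A asks for a single highly effective method. None of the texts available sets a minimum post-dose duration for the second method.

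**The case against.** **The ordinary reading is enough.** Note b joins the treatment period and the time after it in one clause. If stopping on the last dosing day were acceptable, the second half of the clause would do no work, so the natural reading is continuation out to three months. That is probably what the sponsor meant. It supports saying so directly, because the words as they stand also allow an earlier stop.

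**E 12 already protects these women.** It asks for highly effective method(s), in a form that allows the plural, and a weakened hormonal method arguably falls short of that standard. This has some force. However, Table 2 lists the hormonal methods as highly effective, and E 12 leaves the definition to documents outside the body of the protocol.

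**The duration is a clinical decision.** The documents do not say how long the interaction lasts after the last dose, so they do not prove that a second method is needed for a full three months. This stands as a limit. Three months is nevertheless the period the sponsor itself chose for contraception after dosing, and nothing in the documents gives a reason for a shorter one for the second method.

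**Unseen text may cover the point.** The consent form and the SmPC appendix were not available, and either may already give the right duration.

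Three stronger readings should be resisted.

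- A reader might infer that note b contradicts E 12. It does not, because the two rules have different scope and can both be obeyed.
- A reader might express the gap as a number of weeks of missing cover. No text sets a minimum for the second method, so there is no stated rule against which to measure a shortfall.
- A reader might count the methods that carry marker b. The table's layout was damaged when the PDF was read, and markers may have been lost or displaced, so a count would not be reliable.

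**Conclusion.** The point holds as a minor patient-safety wording correction. Note b caps the added method at three months and gives it no minimum, although its purpose is to cover a weakness in the first method during a period that the rest of the plan sets at three months or more. The minimum for the second method should match that period.

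This rests on two assumptions: that the possible interaction matters throughout the three months, which the documents neither state nor deny, and that the consent form does not already set a minimum. The number of women who would be affected cannot be derived from the documents. The endpoint, sample size and analysis are not affected.

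**What to change.** In Appendix A, Table 2, note b, replace *up to* with *at least* and delete the duplicated *after treatment*, so that the post-dose part reads: *for at least 3 months after the last dose of study treatment*. Leave the two-method instruction as it is. Check that the consent form gives the same duration.

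The change can go into the next amendment. Some women will use a second method for slightly longer; no visit, test or analysis is added. If the sponsor holds evidence that a shorter period is enough for the second method, it should state that period as a minimum.

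Two cross-references would help readers but are optional editing: one from section 8.8.3 to note b, and one from E 12 to Table 2. The second adds no entry condition, since Appendix A already ties eligibility to the table.
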